Cushing's syndrome is an endocrine disorder caused by excessive production of glucocorticoids. In 10%-20% of patients this syndrome results from ectopic production of ACTH and very rarely from ectopic CRH production (1-6). Small cell carcinoma of the lung, islet cell tumor of the pancreas, medullary thyroid cancer, pheochromocytoma, and foregut carcinoid tumors are the most common sources of ACTH production (1,2,5,7). The mean age at diagnosis in patients with ectopic ACTH production is 40 years and the male-female ratio is almost 1:1 (1,8). The ectopic source of ACTH production cannot be found in 50% of patients despite aggressive, extensive, and expensive testing (9,10). These patients are at high risk of death due to sepsis, hypertension, gastrointestinal pathology, and metastatic dissemination (8,11). More than 50% of patients with ectopic ACTH production cannot be treated surgically or fail medical therapy and therefore, they finally undergo adrenalectomy with life-long hormone replacement therapy (8). However, if the source of ectopic ACTH production is found before the tumor metastasizes, resection is usually curative. Thus, the ability to image primary and/or metastatic lesions has proved to be the key to successful treatment. Conventional imaging is generally performed with computerized tomography (CT) and magnetic resonance imaging (MRI) of the chest and abdomen. ¹²³I-Metaiodobenzylguanidine (MIBG) is taken up by adrenal tissue and pheochromocytomas and may be useful in identifying this source of ectopic ACTH secretion. As discussed below, other modalities, including somatostatin receptor scintigraphy and various positron emission tomography (PET) ligands, also may be useful in the localization of these tumors.

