Somatostatin receptor scintigraphy using [¹¹¹In-DTPA-D-Phe]-pentetreotide (Octreoscan, OCT), an analog of somatostatin, may identify gastroenteropancreatic tumors, carcinoids, and medullary thyroid carcinomas, all of which express somatostatin receptors (12). The conventional 6 mCi dose of OCT has been reported to localize ectopic ACTH production, at NIH and elsewhere (12-14). De Herder et al. reported a sensitivity of 78% for Octreoscan in patients with ectopic ACTH production (15). However, at NIH, our experience with somatostatin receptor scintigraphy using the conventional dose of 6 mCi of [¹¹¹In-DTPA-D-Phe]-pentetreotide has not been as promising. Detectability of lesions in scintigraphic studies depends not only on the size of the lesion but also on the amount of radioactivity in that lesion. Thus, in the original version of this protocol, we investigated whether a higher dose of radiopharmaceutical could lead to higher concentrations in a lesion and better visualization. In thyroid cancer, it is known that higher doses of ¹³¹I can detect more lesions than lower doses. Furthermore, investigators using high doses of [¹¹¹In-DTPA-D-Phe]-pentetreotide for therapy (180 mCi) have seen more lesions on patients' post therapy scans as compared to their diagnostic scans (16). Analysis of 27 patients with surgically-proven ectopic ACTH-secreting tumors showed a 59% sensitivity for the "low dose" (6 mCi, L-OCT). In patients who had negative L-OCT, "high dose" (18 mCi, H-OCT) had an additional 58% (7/12 patients) sensitivity (17). As a result, the project was amended in 2006 to consider the high dose Octreoscan a medically-indicated test.

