The IRB previously approved an accrual ceiling of 202 for the high dose octreoscan component. That component is no longer a part of the protocol. Eighty-nine patients have enrolled in the protocol. F-DOPA PET was positive in 8 of 17 patients with known tumors and high dose Octreoscan was positive in 7 of 12.

Given these encouraging results, we propose performing F-DOPA in a total of at least 30 patients. The current results imply an estimated success rate of about 55% for each modality; the plausible range for the true success rate ranges from about 26 to 80% using a 95% confidence interval, a very broad range.

Studying a total of 30 patients will allow us the possibility of precluding a true success rate of under 20% (with 95% confidence) if we were to see no additional successes. If there are additional successes in the additional patients the confidence interval for what the true probability of success could be will still be fairly broad. Since limited patients have been evaluated using F-DOPA, we ask that the overall accrual ceiling remain intact and that it be altered based on annual reports of the results. Additionally, we have essentially no data on which to base a sample size calculation for the mifepristone study, and would recalculate accrual limits when such data are available.

Data Collection and Evaluation

Staff in the Departments of Radiology will evaluate the conventional studies. [name] reviews the F-DOPA PET/CT without knowledge of the results of other localization studies. [name] reviews all studies. Data are maintained by the NICHD Clinical Trials DataBase.

The study will be analyzed in collaboration with [name] (Clinical Center Statistics Center). Data are collected and analyzed with regard to the sensitivity, specificity, accuracy, and predictive value for each scan being evaluated. The exploration and pathologic analysis is used as the reference standard. McNemar's test for evaluating paired data will be used (40). In addition to McNemar's test, other approaches to evaluation of the four objectives are below:

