(a) *Compared to other imaging techniques, is the sensitivity and specificity of F-DOPA PET/CT higher in detecting the source of ectopic ACTH production in patients with known and unknown tumor localization?* To determine this, we will calculate the sensitivity, specificity, positive and negative values in patients with proven tumors and compare these with the results from the other modalities. Confidence intervals will be calculated and overlapping results will indicate that the modalities are similar. We cannot perform these calculations for unknown tumors, but can compare the overall percentage of tumors found of all imaged using each technique.

(b) *Does a correlation exist between F-DOPA uptake and the type of tumor, its size and proliferative activity?* To do this, we will evaluate the percent of each type of tumor that has a positive F-DOPA scan. Confidence intervals will be used to compare across tumor types. Univariate logistic regression will be performed using size and mitotic index as the variables.

(c) *Can the administration of mifepristone, 600 mg daily for 10 days, convert a negative standard 6 mCi OCT (L-OCT) to a subsequent positive result?* This will be a descriptive analysis, indicating the percentage of tumors that convert the test to a positive result. A post-hoc analysis will compare this percentage to the historical percentage of tumors that are positive on high but not low dose octreoscan.

(d) *Does gated chest MRI detect more lesions than routine MRI?* A similar approach will be used, to look at the percentage of known tumors that are detected by gated vs routine MRI and comparing confidence intervals around those values.

PHARMACEUTICAL AND RADIATION SAFETY

Pharmaceutical Information: F-DOPA

F-DOPA is a radiolabeled amino acid (^{18}F has a 109 minute half-time). It is approved by the FDA for use under IND # 35513. [name], Chief, PET Department, holds the IND. F-DOPA is produced as outlined in the IND. F-DOPA has been used in many protocols at the NIH and at other centers throughout the world. The formulation is prepared on the day of use and assayed in a dose calibrator. The total amount of F-DOPA will typically be ~2.4 mg and will not exceed 6.5 mg.

Pharmaceutical Information: [^{111}In -DTPA-D-Phe]-pentetreotide

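### Objective (a) takes overlap of separate confidence intervals as showing that modalities are similar, so an inconclusive comparison would be reported as similarity

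*Combined protocol and SAP*

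**What the plan says.** The section Data Collection and Evaluation names McNemar's test for paired data. It then says that, in addition to that test, "other approaches to evaluation of the four objectives are below".

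Under objective (a), which asks whether F-DOPA PET/CT has higher sensitivity and specificity than other imaging, the plan states: "we will calculate the sensitivity, specificity, positive and negative values in patients with proven tumors". These are to be compared with the other modalities by this rule: "Confidence intervals will be calculated and overlapping results will indicate that the modalities are similar".

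No interval method, confidence level or similarity margin is given for this objective. No order of precedence is given between the overlap rule and McNemar's test.

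Objective (d), gated against routine chest MRI, is to be handled in a similar way by comparing intervals around each percentage. It does not restate that overlap means similar.

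On size, Justification of the number of subjects reports that "F-DOPA PET was positive in 8 of 17 patients with known tumors" and adds: "we propose performing F-DOPA in a total of at least 30 patients".

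**The concern.** Overlap of two wide intervals shows that the data cannot separate the modalities. It does not show that they perform alike. The rule turns a lack of information into a positive finding, and the smaller the sample, the more readily it does so.

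Two features make it lax. First, each interval describes one modality alone, although the same patients have both scans and the within-patient comparison carries the information. Second, requiring two 95% intervals to separate is much stricter than a 5% test. For independent samples with equal standard errors it corresponds to p = 2 × (1 − Φ(1.96 × √2)) = 0.0056.

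At stake is the reported answer to the protocol's first question. An inconclusive comparison would be published as similarity. Less often, similarity would be reported on data where the planned paired test shows a difference.

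**Working it through.** **Inputs.** F-DOPA 8/17 in known tumors (Justification of the number of subjects). Standard-dose Octreoscan 59%, from the Introduction: "Analysis of 27 patients with surgically-proven ectopic ACTH-secreting tumors showed a 59% sensitivity". These come from different patient sets. Assumed, because the plan is silent: 95% two-sided intervals, and exact two-sided McNemar at 0.05.

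**The plan's own interval.** The sample-size text gives about 26 to 80%. Wilson intervals are 26.2 to 69.0% for 8/17 and 32.0 to 80.7% for 7/12 (high-dose Octreoscan). The stated range matches only the outer limits of these two together. Wilson is therefore the best guess at the method used there, but nothing fixes it for objective (a), so three methods are shown.

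**Step 1: intervals for 8/17 = 0.471.**
- Wilson: centre (0.4706 + 3.8416/34)/(1 + 3.8416/17) = 0.476; half-width 1.96 × √(0.2491/17 + 3.8416/1156)/1.226 = 0.214; interval 0.262 to 0.690.
- Wald: 0.471 ± 1.96 × √(0.2491/17) = 0.233 to 0.708.
- Clopper-Pearson: 0.230 to 0.722.

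**Step 2: which comparators k/17 overlap?**

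| Method | Counted as similar | Limiting intervals |
|---|---|---|
| Clopper-Pearson | 1/17 to 16/17 | 1/17: 0.001–0.287; 16/17: 0.713–0.999 |
| Wilson | 1/17 to 15/17 | 1/17: 0.010–0.270; 15/17: 0.657–0.967 |
| Wald | 2/17 to 14/17 | 2/17: 0–0.271; 14/17: 0.642–1 |

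**Step 3: can the rule contradict McNemar?** With b and c the discordant counts, exact p = 2 × P(X ≤ min(b, c)), X ~ Binomial(b + c, ½).
- 8/17 against 1/17. The comparator's single positive either is or is not F-DOPA positive, so only two tables exist. 7–0 gives 2/128 = 0.016; 8–1 gives 2 × (1 + 9)/512 = 0.039. Both are below 0.05, yet the intervals overlap under Clopper-Pearson and Wilson (not Wald).
- 23/30 against 14/30. The intervals overlap under all three methods (Clopper-Pearson 0.577–0.901 and 0.283–0.657; Wilson 0.591–0.882 and 0.302–0.639; Wald 0.615–0.918 and 0.288–0.645). McNemar p is 0.004 at 9–0, 0.049 at 13–4 and 0.093 at 16–7, so the conflict depends on the pairing.

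**Step 4: how often?** The paired 2×2 table was enumerated exactly at n = 17, from the least favourable pairing (fewest tumors positive on both scans) through independence to full nesting, with Clopper-Pearson or Wilson intervals.

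| True rates | Chance of a similar verdict |
|---|---|
| 47% in both | 96–100% |
| 59% against 47% | 94–100% |
| 80% against 50% (assumed) | 77–96% |

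With Wald intervals the last row is 71–81%.

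The chance that the intervals overlap and McNemar gives p ≤ 0.05, at 59% against 47%, is 0–4% at n = 17, 0–8% at n = 23 and 0–14% at n = 30. The 30 planned patients are not 30 proven tumors, since the Introduction says: "The ectopic source of ACTH production cannot be found in 50% of patients". If half of 13 further patients had a proven tumor, n would be about 17 + 6.5, or 23; n = 30 is an upper illustration.

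**The case against.** The strongest reply is that the paired test is already planned. McNemar's test is named first and the interval comparisons come in addition, so the overlap sentence may be only a descriptive gloss. A reader might go further the other way and infer that the plan ignores pairing altogether; the documents do not support that. What stands is narrower: no precedence is stated, the overlap sentence is the only criterion given for concluding similarity, and a non-significant McNemar result would not justify that conclusion either.

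A second reply is that the practical difference is small. At 59% against 47% with 17 tumors, exact McNemar rejects only about 1 to 6% of the time, so in some 94 to 99% of datasets the paired test also shows no difference and only the label changes. That is correct. The limit is sample size, which the plan openly acknowledges by calling its current interval very broad. It is also why the label matters: inconclusive is accurate and similar is not.

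A third reply is that objective (a) asks whether F-DOPA is higher, and for that question the rule usually errs towards not claiming superiority. This is fair, but the sentence does more than withhold a claim; it makes one.

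Objective (d) is weaker support. It compares separate intervals, and a reader might infer that the overlap rule carries over, but the text does not say so.

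**Conclusion.** The sentence is wrong as written and should be replaced. Its main effect is to report an inconclusive comparison as similarity. At 17 tumors that verdict is nearly certain when there is no true difference, and still has a 77 to 96% chance (Clopper-Pearson or Wilson) under an assumed 30-point difference, so it carries little information.

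Three stronger readings do not hold:
- The 1/17 to 16/17 range is not an observed comparison. The documents give no comparator results in those 17 patients and no interval method. The 17 are known tumors studied with F-DOPA PET, and the Introduction says PET/CT was not available earlier. The range illustrates how wide the rule is.
- Frequent contradiction of McNemar is not established. It is 0 to 4% at 17 tumors with the documents' rates, which themselves come from different patient sets. Much larger figures need true rates that the documents do not give, together with favourable pairing.
- Nothing in the documents ties treatment or accrual to the similarity verdict.

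The conclusion about the label holds under all three interval methods.

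**What to change.** Delete the overlap sentence. State that, in patients with a proven tumor and both scans, exact McNemar at a stated alpha, with a 95% confidence interval for the paired difference (for example Tango or Newcombe for paired proportions), decides the sensitivity comparison, and the specificity comparison where it can be estimated. Keep single-modality intervals as description, with the method named. Report a non-significant result as no difference shown, or inconclusive, and claim similarity only against a margin set in advance.

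Use the same paired comparison for gated against routine MRI in objective (d), in patients who had both.

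The cost is a wording change in the analysis section and a little extra analysis of the same data, with no extra patients or scans. The downside is that many results will read as inconclusive where the present text would call them similar.

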We found that F-DOPA PET substantiated a lesion seen on CT and/or MRI scan in 6 of 11 patients, including some with questionable results on conventional imaging. We amended the protocol in 2008 to administer carbidopa, 200 mg, one hour before the study. [name] has found that this strategy improves tumor detection of pheochromocytoma, presumably by inhibiting decarboxylation of the tracer. This amendment will now allow us to perform FDOPA PET/CT, which was not available previously.

The project was amended in 2004 regarding the routine chest MRI scans. We initially obtained images on a 0.5 T magnet using, using STIR, T1 and T2 images. Subsequently a 1.5 T magnet replaced the lower strength magnet and STIR images were not obtained. Recently a 3.0 T magnet has become available with image acquisition gated to the EKG R-R interval so that artifact from cardiac motion is reduced. Our collaborator [name] has performed T1 and T2 sequences using this approach with excellent resolution of mediastinal and chest structures. Increased strength of magnetic field compared to conventional 1.5T MRI allows for a stronger signal and therefore improved signal to noise ratio. Free breathing techniques are used to avoid breath holding, which may be difficult for those patients with volume overload. The combination of higher signal and decreased motion artifacts should significantly improve resolution allowing for better delineation of small lesions that may be responsible for ectopic ACTH production. To test this, we have added these sequences.

We wish to clarify the use of chest CT scans, as the available modalities have changed. A “surgical chest protocol CT” (which involves thin (1-2mm) cuts throughout the thorax) will be obtained at each visit.

For the initial imaging, gated “cardiac CT” will be obtained as well to look for retrocardiac lesions that can be obscured by non-gated routine CT. However, because of the amount of radiation, we will obtain this scan only at the initial visit, unless there is a subsequent clinical suspicion of a retrocardiac lesion.

OBJECTIVES

Specific questions to be addressed:

F-DOPA PET/CT

(a) Compared to other imaging techniques, is the sensitivity and specificity of F-DOPA PET/CT higher in detecting the source of ectopic ACTH production in patients with known and unknown tumor localization?

(b) Does a correlation exist between F-DOPA uptake and the type of tumor, its size and proliferative activity?

Octreoscan

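### Objective (b) asks about F-DOPA uptake, but its analysis uses only scan positivity, a coarse substitute that mixes reader detection with uptake and discards information

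*Combined protocol and SAP*

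**What the plan says.** The Objectives section, F-DOPA PET/CT item (b), and the matching item under Data Collection and Evaluation both ask: "Does a correlation exist between F-DOPA uptake and the type of tumor, its size and proliferative activity".

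The analysis given for it has three parts:
- Tumor type: "we will evaluate the percent of each type of tumor that has a positive F-DOPA scan".
- Comparison between types: "Confidence intervals will be used to compare across tumor types". No test is named.
- Size and proliferation: "Univariate logistic regression will be performed using size and mitotic index as the variables". The outcome is not named. The model requires a binary one, and scan positivity is the only one offered.

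Size and mitotic index are not said to be categorised, so only the uptake side is reduced to two levels. No section defines, records or analyses a graded uptake measure.

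No power or sample size is given for (b). Under Justification of the number of subjects the relevant figures are "we propose performing F-DOPA in a total of at least 30 patients" and "F-DOPA PET was positive in 8 of 17 patients with known tumors".

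**The concern.** Uptake is a graded quantity. A positive or negative call is a reader's decision about whether a lesion was seen. The Introduction itself says, of scintigraphy, that whether a lesion is detected depends on its size as well as on the radioactivity in it. If the same applies to PET, positivity could be associated with size even where uptake is not, and a small tumor read as negative could be taken for a tumor with low uptake.

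The second cost is information. Splitting a graded outcome in two wastes data, which matters in a sample of about 30. At stake are the interpretation and precision of objective (b). Objective (a) and safety are not affected.

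**Working it through.** **The plan's own figure.** There is none for (b). The only F-DOPA planning statement is that 30 patients allow "precluding a true success rate of under 20% (with 95% confidence) if we were to see no additional successes", and it concerns the success rate. It does not reproduce: 8/30 has an exact lower limit of 12.3% (two-sided 95%) or 14.0% (one-sided 95%). That is a separate matter and nothing below depends on it.

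**Inputs from the documents.** N = 30 F-DOPA patients. Positive rate 8/17 = 47%. The plan also says "The current results imply an estimated success rate of about 55% for each modality"; using 55% instead moves the power results by about 2 points at most.

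**Assumptions.** Correlation 0.4 to 0.5 between uptake and the predictor, bivariate normal, two-sided 5%, and every tumor proven and measurable. The documents give no correlation and no tumor-type mix.

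**Step 1: information kept by the binary outcome.** Relative efficiency = φ(c)² / [p(1−p)], where c is the normal cut-point giving positive rate p.
- p = 0.47 gives c = 0.075 and φ(c) = 0.398.
- 0.398² / (0.47 × 0.53) = 0.158 / 0.249 = 0.635.
- 30 × 0.635 ≈ 19, so 30 tumors scored positive/negative carry roughly the information of 19 with uptake measured.

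**Step 2: tumors needed for 80% power at correlation 0.5.** Fisher z: n = [(1.960 + 0.842) / atanh(0.5)]² + 3 = (2.802 / 0.549)² + 3 ≈ 29.0, rounded up to 30. With the binary outcome, 30 / 0.635 ≈ 48.

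**Step 3: power by simulation.** The continuous range runs from Spearman (lower) to Pearson (upper). The binary columns are the planned univariate logistic regression.

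| Proven tumors | Correlation | Continuous uptake | Logistic, likelihood ratio | Logistic, Wald |
|---|---|---|---|---|
| 30 | 0.4 | 55-59% | 45% | 35% |
| 30 | 0.5 | 77-83% | 64-66% | 56% |
| 17 | 0.5 | 51-58% | 42-44% | 14% |

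At 30 tumors the gap to the likelihood-ratio test is 55 − 45 = 10 points at the least and 83 − 66 = 17 at the most. The likelihood-ratio test is slightly liberal at these sizes (type I error about 6-7%) and the Wald test conservative (about 1-4%), so the fair comparison lies between them.

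**Step 4: negative tumors at background.** Uptake is set to a floor for all scan-negative tumors (N = 30, correlation 0.5): Spearman 66%, censored (Tobit) regression 72%, planned logistic by likelihood ratio 66%. The gain is 0 to 6 points.

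**Step 5: scanner and carbidopa.** The Introduction says carbidopa was added in 2008 and that PET/CT was not available before the current amendment, so there may be three acquisition settings.
- Adjusting for three settings at N = 30, correlation 0.5: power stays at about 80%.
- Restricting to PET/CT: if the total is 30 and the 17 known-tumor scans predate PET/CT, 30 − 17 = 13 remain, and power is about 37-39%. That is below the planned logistic regression at N = 30.

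**Step 6: two tumor types one standard deviation apart.** With 15 tumors each, power is 78% on continuous uptake and 56% on positive rates. With 8 each, it is 52% and 32%.

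**The case against.** The strongest case for the plan has four parts.

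- **Purpose.** The study is about localization, for which visible uptake is what matters clinically. Objective (b) is subsidiary and carries no power claim. Positivity is a crude form of uptake, so regressing it on size and mitotic index does test a related association. This stands. A reader might infer that the plan cannot address (b) at all; the documents do not support that.
- **Conditional gain.** Nothing in the documents shows that graded uptake can be read in scan-negative tumors, and at 8/17 positive about half would be in that group. This stands, and Step 4 gives the consequence.
- **Sample size.** Size and mitotic index need resected tumor, and the Introduction says the source is not found in about half of patients. Thirty proven tumors may be optimistic, and with fewer both analyses are weak. This stands.
- **Resolution.** Partial-volume loss lowers measured uptake in small tumors as well, so a size-uptake correlation can carry the same artefact. This stands: the change reduces dependence on the reader's threshold but does not remove the problem.

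Scanner and carbidopa differences are a weaker defence. They can shift positivity too, and the plan does not adjust for them.

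A reader might also carry over the overlap-means-similar rule that the plan states for objective (a). For two types of 15 tumors one standard deviation apart, requiring exact intervals not to overlap would give only 15% power. The plan does not state that rule for (b), so the figure should not be held against it.

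**Conclusion.** The mismatch holds on the text: the question is about uptake and the planned outcome is scan positivity. For tumor type this is explicit. For size and mitotic index it is inferred from the choice of logistic regression.

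Under the assumptions in the working, measured uptake gains about 10 to 17 points of power over the likelihood-ratio logistic test at 30 proven tumors, and more against Wald. The gain could be close to nil if negative tumors are all at background. A reader might infer a fixed loss of nearly 20 points; the documents do not support that, because they give no effect size and because the gain depends on how scan-negative tumors measure. Even with no gain in power, a result on positivity should not be reported as a result on uptake.

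This is a worthwhile, inexpensive improvement to a subsidiary objective. It would not make (b) reliable for weak correlations.

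**What to change.** 1. For pathologically proven tumors, define the outcome for (b) as lesion uptake, for example maximum standardised uptake value or tumor-to-background ratio. Measure it on existing images at the proven site, including scans read as negative, and only after the masked read is complete.
2. Analyse uptake by rank correlation or linear regression on size and mitotic index, and compare it across tumor types.
3. Adjust or stratify for scanner (PET versus PET/CT) and carbidopa. Do not restrict to PET/CT.
4. Treat lesions at background as tied or censored, and state that partial-volume loss in small tumors can itself produce a size-uptake association.
5. Keep the positive/negative summaries and logistic regression as secondary, with the outcome named.

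The cost is measurement time on stored images, a short change of wording, and some remaining heterogeneity between scanners. No new scan or radiation is needed. If uptake will not be measured, the minimum is to word the conclusions for (b) as being about scan positivity.

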Between 10% and 20% of patients with hypercortisolism (Cushing syndrome) have ectopic production of adrenocorticotropin hormone (ACTH) that causes cortisol excess. In approximately 50% of these patients, the source of ACTH cannot be found despite very detailed and extensive examination including imaging studies such as computed tomography scanning, magnetic resonance imaging, and octreotide scan (Octreoscan) using the standard dose of indium- 111 pentetreotide ([¹¹¹In-DTPA-D-Phe]-pentetreotide). The sensitivity and specificity of these imaging studies depends on anatomic alterations and/or the dose and adequate uptake of radiopharmaceutical. In contrast, positron emission tomography (PET) has the ability to detect pathologic tissue based on physiologic and biochemical processes within the abnormal tissue. This protocol tests whether [¹⁸F]-L-3,4-dihydroxyphenylalanine (¹⁸F-DOPA) can be used to localize successfully the source of ectopic ACTH production. In addition the study examines whether administration of the glucocorticoid antagonist mifepristone can improve the sensitivity of the standard dose Octreoscan. Eligible patients participating in this arm of the study will have a second standard dose

scan. Others will receive a higher dose octreoscan instead.

INTRODUCTION

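### Objective (b) names no estimator or test for its logistic regressions; with few tumors the default maximum-likelihood fit overstates a real slope on average and its Wald and likelihood-ratio tests miss 5%, so specify Firth penalised likelihood

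*Combined protocol and SAP*

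**What the plan says.** All references are to the combined protocol and SAP, mainly its Analysis of the Study part.

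- Objective (b), under Data Collection and Evaluation, asks: "Does a correlation exist between F-DOPA uptake and the type of tumor, its size and proliferative activity". For the two continuous covariates the whole plan is one sentence: "Univariate logistic regression will be performed using size and mitotic index as the variables". It states no estimator, test, significance level, interval method, effect size or rule for separated data. The outcome is taken here to be scan positivity, because the sentences before it concern the percentage of tumors with a positive scan.
- The same section sets the truth standard: "The exploration and pathologic analysis is used as the reference standard".
- Justification of the number of subjects gives the data so far, "F-DOPA PET was positive in 8 of 17 patients with known tumors", and the target, "we propose performing F-DOPA in a total of at least 30 patients". It also asks that the accrual ceiling be kept and revised in the light of annual reports.
- The opening summary says of ectopic cases: "In approximately 50% of these patients, the source of ACTH cannot be found".

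**The concern.** Mitotic index needs tissue, so the regression can use only patients whose tumor was found and removed. Logistic regression without further qualification usually means maximum likelihood with whichever test the software prints. With a few dozen binary outcomes or fewer, that default has known weaknesses: slopes biased away from zero, a Wald test that rarely rejects, a likelihood-ratio test that rejects too often, and, when a skewed covariate splits positives from negatives perfectly, no finite estimate.

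Two analysts following the plan on the same data could therefore work at different true error rates, and the test could be chosen after the results are seen. The reported odds ratio for size or mitotic index would tend to be too large.

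**Working it through.** **Stated figure.** The plan gives no sample size, power or level for (b), so there is nothing to reproduce.

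**Inputs from the documents.** 17 known tumors, 8 positive: 8/17 = 47%. The plan elsewhere says "The current results imply an estimated success rate of about 55% for each modality". If the 17 count towards the 30 and half of the remaining 30 - 17 = 13 patients have a tumor found, the usable number is 17 + 0.5 x 13 = 23.5, or about 23-24. It is lower if patients with occult tumors have already been scanned, and higher if accrual passes 30.

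**Assumptions.** Two-sided 5% level (the only level nearby is the phrase "using a 95% confidence interval"). True log odds ratio per SD of 0, 0.5 or 1.0, the last being an odds ratio of exp(1.0) = 2.7. Covariate normal, lognormal (log-SD 0.7) or overdispersed count (mean 2). Positivity 47%, with 70% as a sensitivity case.

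**Method.** Data were generated from logit P(positive) = b0 + b1 x, with x in SD units: 20,000 data sets per setting in the main run and 12,000 in a sensitivity run. Maximum likelihood (ML) maximises l(b). Firth maximises l*(b) = l(b) + 0.5 log|I(b)|, where I is the information matrix. The tests were:

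- Wald: (b1 estimate / SE) squared
- likelihood ratio (LR): 2[l(full) - l(b1 = 0)]
- score: equals n r^2 for one covariate, with r the correlation of x with the outcome
- penalised LR: the LR formula with l*

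Separated data sets were left out of the ML means and counted as non-rejections for Wald.

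**Main run, 47% positive (ranges are over covariate shapes).**

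| Quantity | n = 17 | n = 30 |
|---|---|---|
| ML mean slope, true 1.0 | 1.39-1.49 | 1.17-1.23 |
| ML median slope, true 1.0 | 1.15-1.18 | 1.07-1.10 |
| ML mean slope, true 0.5 | 0.67-0.76 | 0.58-0.63 |
| Firth mean slope, true 1.0 | 1.02-1.04 | about 1.01 |
| Firth median slope, true 1.0 | 0.81-0.91 | 0.90-0.94 |
| Type I error, ML Wald | 0.7-1.2% | 2.0-3.4% |
| Type I error, ML LR | 6.9-7.8% | 5.7-6.9% |
| Type I error, score | 4.3-5.2% | 4.6-5.0% |
| Type I error, penalised LR | 3.4-4.0% | 3.9-4.4% |
| Type I error, Firth Wald | 0.2-0.5% | 1.1-1.9% |
| Power at slope 1.0, ML LR | 37-47% | 57-68% |
| Power at slope 1.0, penalised LR | 24-37% | 48-63% |

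**Size of the bias.** At n = 17 and true slope 1.0, the mean excess is 39-49%. On the odds-ratio scale the mean slope corresponds to exp(1.39) = 4.0 to exp(1.49) = 4.4, against 2.7. At n = 30 the excess is 17-23%, and at n = 60 it is 8-11% (mean 1.08-1.11). With a true slope of 0 the mean stays within 0.03 of 0. A further run (6,000 data sets per setting, true slope 1.1) gave ML means of 1.3-1.6 at n = 17. That is 1.3/1.1 - 1 = 18% to 1.6/1.1 - 1 = 45%. It also gave Firth means of 1.11-1.14, 95-97% coverage of the profile interval, and root mean squared error of 0.86 for Firth against 1.56 for ML (normal covariate).

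**Sensitivity run (normal and count covariates, 47% and 70% positive).** Type I error at n = 17 and n = 30 respectively:

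- Wald: 0.5-1.4% and 1.9-3.6%
- LR: 7.5-8.3% and 6.2-6.9%
- score: 4.4-5.8% and 4.4-5.6%
- penalised LR: 3.3-4.7% and 3.8-4.8%

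With a count covariate and 70% positive, the ML mean for a true 1.0 was 1.36 at n = 30 and 1.18 at n = 60, so bias in that setting is larger than at 47%.

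**Separation (true slope 1.0, 47% positive).** 0.4-1.5% at n = 17, at most 0.03% at n = 30, and 4-10% at n = 11. At n = 17 with counts and 70% positive it was 7.3%.

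**The case against.** **The plan has not chosen a faulty method.** It names no estimator or test, Firth regression is still univariate logistic regression, and a statistics group is involved. This stands: the default reading is an inference, and the defect is under-specification.

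**A reader might infer that every test from the ordinary model is off level.** That is not so. The score test is close to 5% and needs no change of estimator. It does not correct the odds ratio.

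**A reader might infer that Firth repairs everything for nothing.** It does not. At about half positive, the penalised LR test has 2-5 points less power than the score test and, at n = 17, 9-14 points less than the LR test. Most of the latter is the price of removing inflation: with critical values set to a true 5%, power is 36.7% for LR and 36.6% for penalised LR (normal covariate, n = 17, 47% positive). A real loss remains with counts and 70% positive (20.3% against 14.5%). There the nominal gap to LR is 27.7 - 10.8 = 16.9 points, although the penalised test is slightly ahead of the score test (10.8% against 9.9%). At n = 17, 47% positive and x = +1 SD, a true probability of 0.70-0.72 is predicted by Firth as 0.67-0.68.

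**A reader might take 30 as the largest number of tumors.** It is a minimum number of patients scanned. The bias is larger with fewer tumors and modest at 60 when half are positive.

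**Objective (b) drives no stated decision.** This stands too, and it limits the importance of the point.

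**Conclusion.** The concern holds as a low-cost improvement to an under-specified analysis. Across the runs, with about half of scans positive, ordinary maximum likelihood overstates a non-zero slope on average by about 20-50% at 17 tumors, 15-25% at 30 and 10% at 60. Its Wald test is conservative and its likelihood-ratio test mildly liberal. Firth estimation removes nearly all of the mean bias and always gives a finite estimate; its penalised LR test runs at about 3-5%.

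These sizes rest on the assumed level, effect sizes, covariate shapes and positivity, none of which the documents give for (b). The documents do not support saying that an effect of size or mitotic index will be overstated whatever the truth: there is no bias under the null, and the median excess at n = 17 is smaller (15-18%) than the mean excess. Frequent separation cannot be asserted either, because it depends on the assumed distribution. No estimator cures the low power: with the penalised LR test it is 24-37% at 17 tumors and 48-63% at 30, for an odds ratio of 2.7 per SD and 47% positive.

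**What to change.** In item (b) of Data Collection and Evaluation, state before analysis that:

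- both univariate models are fitted by Firth penalised likelihood;
- odds ratios are reported with profile penalised-likelihood intervals and tests, not Firth Wald results;
- objective (b) is exploratory;
- if predicted probabilities are reported, the intercept is corrected.

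A score or exact test is an acceptable alternative for testing, but it leaves the odds-ratio bias in place.

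The change takes a few sentences, needs no new data and uses standard software. The statistical costs are those set out above: a slightly conservative test, usually a few points less power than the score test, a median slope below the truth and, unless corrected, predictions drawn towards 0.5.
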